10.1.11	Conflict of Interest Policy	57
10.2	Abbreviations	57
10.3	Protocol Amendment History	59
11	REFERENCES	60

STATEMENT OF COMPLIANCE

[figure not shown]
The trial will be conducted in accordance with International Conference on Harmonization Good Clinical Practice (ICH GCP), applicable United States (US) Code of Federal Regulations (CFR), and the NIH National Institute of Diabetes and Digestive and Kidney Diseases (NIDDK) Terms and Conditions of Award. The Principal Investigator (PI) will assure that no deviation from, or changes to the protocol will take place without prior agreement from the abbreviated Investigational Device Exemption (IDE) sponsor, funding agency and documented approval from the Institutional Review Board (IRB), except where necessary to eliminate an immediate hazard(s) to the trial participants. All personnel involved in the conduct of this study have completed Human Subjects Protection and ICH GCP Training.

The protocol, informed consent form(s), recruitment materials, and all participant materials will be submitted to the IRB for review and approval. Approval of both the protocol and the consent form will be obtained before any participant is enrolled. Any amendment to the protocol will require review and approval by the IRB before the changes are implemented to the study. All changes to the consent form will be IRB approved; a determination will be made regarding whether a new consent needs to be obtained from participants who provided consent, using a previously approved consent form.

1 PROTOCOL SUMMARY

1.1 SYNOPSIS

Table 1: Study Synopsis

Study Title:	Randomized Crossover Euglycemic Clamp Study in Adult Patients with Type 1 Diabetes to Assess Pharmacokinetics and Pharmacodynamics of Subcutaneously Infused Insulin Using an Investigational Extended Wear Continuous Subcutaneous Insulin Infusion Cannula Compared to a Commercial Infusion Set
Short Title:	PK/PD of an Extended Wear Infusion Set for CSII in T1DM Patients (“PEXIS”)
Device Description:	
The Capillary Biomedical, Inc. (CapBio) Achilles infusion set is a sterile, non-pyrogenic, single use device for continuous subcutaneous insulin infusion (CSII). Achilles infusion sets are designed to be used with commercially available infusion pumps (e.g., Medtronic Paradigm). The use of the Achilles infusion set is identical to the commercially available MiniMed Silhouette control device. The investigational Achilles infusion set and control Silhouette devices differ only in the materials (coil-reinforced soft polymer vs Teflon) and construction (one distal and three side ports vs single distal port, respectively) of the indwelling cannula.
 
Each infusion set has two basic components: the infusion set body with an indwelling cannula and a tubing set for connection to the infusion pump reservoir. The Achilles infusion set body is provided individually packaged in a sterile pouch. The infusion set body is then connected to the tubing set from a commercially available infusion set with the proprietary pump reservoir connector (e.g., Medtronic Paradigm) for use with specific infusion pumps.

Device Illustration:	
  
 
CONTENTS
 
 A. Needle guard B. Soft cannula C. Adhesive tape D. Introducer needle E. Cannula housing F. Tubing G. Connector needle H. Circular protective cap I. Disconnect cover 
 
 
See document 710-1021-00 Achilles Infusion Set, Instruction For Clinical Use.

Indication/Intended Use	The Achilles Infusion Set is intended for the subcutaneous (SC) infusion of medication, including insulin, from an external infusion pump.
Study Description:	This study has been designed as a prospectively enrolled, randomized sequence, 2-way crossover study of device performance, tolerability and safety of the investigational Achilles infusion set or commercial infusion set during two 7-day home use periods with 4 in-clinic euglycemic clamp sessions during each of the 7-day periods. After a wash-out period, patients will cross over into the investigational or control group, respectively.

Hypothesis:	
We hypothesize that the rate of decline or slope (s) of natural logarithm of the area under the glucose infusion rate curve $AUC_{0-300(GIR)}$ over wear time (=4 clamp experiments) will be less using the investigational Achilles infusion set compared to the commercial control.
 
Statistical hypotheses:
 
 Null Hypothesis: There is no difference in the population mean rates of decline for the Achilles and control infusion sets, as measured by the slope (s) contrast for the $\ln(AUC_{0-300(GIR)})$ assessed over study days DOI (day 0), day 3, day 5, and day 7. $H_0: s_{control} = s_{Achilles}$ 
 Alternative Hypothesis: The rate of decline (slope coefficient s) for the Achilles infusion set is less that the corresponding rate for control. $H_A: s_{control} < s_{Achilles}$
Primary Objective	To assess the reliability of delivery using the investigational Achilles infusion set by evaluating the rate of decline of the glucose lowering effect of insulin from DOI through day 7 (8 th calendar day of wear) compared to the commercially available control.
Primary Endpoint	Rate of decline (s) over wear time (DOI, day 3, day 5, day 7) of the natural logarithm of the area under the glucose infusion rate curve [$\ln(AUC_{0-300(GIR)})$]
Secondary Objective 1:	To assess pharmacodynamic (PD) parameters within and across treatments following subcutaneous insulin delivery using Achilles vs Teflon control set on DOI and days 3, 5 and 7 post insertion.
Secondary Endpoints 1:	
Mean differences (within treatments over time and between treatments at specified time points) in:
 
 Time-to-Maximum Glucose Infusion Rate (GIR) ($t_{max(GIR)}$) Time to half-maximal GIR, both early and late ($t_{50(GIR),early}$ & $t_{50(GIR),late}$) Onset of action as measured by a drop of blood glucose (BG) by 5 mg/dL Duration of insulin action (calculated the same as MRT for PK) GIR_{max} Area under the GIR curve ($AUC_{0-t(GIR)}$), both absolute and as a percentage of total $AUC_{0-\infty}$ and Coefficient of Variation (CV) of $AUC_{0-t(GIR)}$, where $t = 5, 10, 15, 20, 30, 45, 60, 90, 120, 150, 180, 210, 240,$ and 300 min 
Other PD parameters may also be calculated.

Secondary Objective 2:	To assess pharmacokinetic (PK) parameters within and across treatments following subcutaneous delivery using Achilles vs Teflon control set on DOI and days 3, 5, and 7 post insertion.
Secondary Endpoints 2:	
Mean differences (within treatments over time and between treatments at specified time points) in:
 
 • Early exposure ($AUC_{0-60min}$) • Mean-residence time (MRT) of insulin • Maximum Insulin concentration (C_{max}) • Time-to-Maximum Insulin Concentration (t_{max}) • Time-to-50% Maximum Insulin Concentration [$t_{50,early}$ & $t_{50,late}$], both early (i.e. before C_{max}) and late (i.e. after C_{max}) • $AUC_{(0-t)}$ (both absolute and as a percentage of $AUC_{(0-300)}$) and Coefficient of Variability (CV) $AUC_{(0-t)}$ where $t = 3, 6, 9, 12, 15, 20, 25, 30, 35, 40, 45, 50, 60, 70, 80, 90, 105, 120, 150, 180, 210, 240$ and 300 min 
Other PK parameters may also be calculated.

Secondary Objective 3:	To assess continuous glucose monitoring (CGM) data, comparing data within and across treatments.
Secondary Endpoints 3:	
 • Mean daily time in range (70-180 mg/dL), DOI through Day 7 inclusive • Mean daily time in target (70-140 mg/dL), DOI through Day 7 inclusive • Mean and median daily glucose, DOI through Day 7 inclusive • Glucose variability (%CV), DOI through Day 7 inclusive • Mean daily time ≤ 70 mg/dL, < 54 mg/dL, DOI through Day 7 inclusive • Mean daily time > 140 mg/dL, > 180 mg/dL, > 240 mg/dL, DOI through Day 7 inclusive • Other CGM metrics may also be calculated
Secondary Objective 4:	To assess performance of investigational infusion set on DOI through 7 for each treatment
Secondary Endpoints 4:	
 • Proportion of investigational CSII sets that did not fail on each day of use. • Mean difference across treatments in time to device failure • Mean difference across treatment in incidence of pump bolus occlusion alarms • Mean difference across treatment in incidence of pump basal occlusion alarms

Safety Objectives:	To assess Achilles infusion set safety and tolerability from DOI through day 7 for each treatment
Safety Endpoints:	
 • The occurrence hyperglycemia (glucose >250 mg/dL) not responsive to a pump bolus dose where response to the bolus is defined as a fall of at least 50 mg/dL in blood glucose within one hour, • The occurrence of hyperglycemia (glucose >250 mg/dL) after prolonged fasting (e.g. overnight or more than 5 hours following a meal), not associated with acute intercurrent illness, but with a concurrent ketone level ≥ 0.6 mmol/L. • Localized infection or inflammation of greater than 1.0 cm in diameter at the infusion site • Occurrence of an insulin pump occlusion alarm signal • Cannula dislodgement from subcutaneous space, • Cannula malfunction (inability to pierce skin, bending, kinking, fluid leakage or other malfunction that might impact insulin infusion) • Mean visual analog scores (VAS) scores (0-100 mm) from Day of insertion through Day 7 of use • Mean difference of VAS scores (0-100mm) of CSII investigational sets and CSII control sets • Descriptive statistics of per subject term, severity, adverse device effects, and frequency of adverse events for each treatment • Descriptive statistics of per subject incidence of unanticipated adverse device effects
Study Population:	
Up to 30 adult participants, with the goal of having approximately 24 completers, may be enrolled, ages 18–70, diagnosed with Type 1 diabetes mellitus (T1DM) who have ≥ 6 months experience using rapid-acting insulin analog delivered via Medtronic MiniMed insulin pump and infusion sets. Only Medtronic pump models 530 and higher may be used.
 
Study participants will be drawn from existing T1DM patient populations meeting the study eligibility at each study center and from referral practices.

Phase:	Phase 1b
Description of Sites /Facilities Enrolling Participants:	This study will be conducted at no more than 5 centers in the United States. Each site will be qualified to conduct insulin treatment studies per a standardized euglycemic clamp protocol.


Description of Study Intervention:
	
Existing patient populations at each study center will be screened for study eligibility within 28 days of planned study enrollment. Participants without prior experience using the Dexcom G6 will be allowed up to 14 days of a run-in period to familiarize themselves with the CGM device. Eligible participants will complete written informed consent and be assigned a unique study ID.
 
Eligible participants will be randomized for Treatment Period A to either the Achilles investigational cannula or a Medtronic Silhouette control cannula using commercially available tubing, insulin lispro, insulin pumps and continuous glucose monitoring (CGM) equipment. After 2±1 week of washout each participant will enter Treatment Period B for a second 7-day period of catheter wear-time using the other infusion set.
 
On Day of Insertion (Day 0), participants will have the investigational Achilles infusion set or the control infusion set inserted by a qualified professional during a clinic visit. Participants will undergo training and be provided written instructions if infusion set change out is required during the 7-day wear period.
 
At the start of the study, participants will be provided with an insulin lispro vial (Humalog®, Eli Lilly and Co., Indianapolis, IN), a 23” tubing set compatible with the Achilles infusion set and Ascencia Contour Next glucose monitor plus test strips. Participants will also wear a study-provided Dexcom G6® (study continuous glucose monitor, to be used in real time mode) for the duration of the study. Participants will manage routine basal/bolus insulin therapy using these supplies and their current insulin pump for two home use wear periods of up to 7 days each. Finally, an Abbott Precision Xtra ketone monitor plus test strips will be provided for use in the event of hyperglycemia >250 mg/dL.
 
Visual inspection and photographic documentation of the Achilles and the comparator infusion set insertion site will be recorded at Day 0. Participants will be asked to conduct daily insertion site visual inspection and report/record site reactions, glycemic intervals and/or the need for infusion set change out (Days +1 to +7).
 
During a 7-day wear period, participants will undergo 4 in clinic euglycemic glucose clamps [Day of Insertion (DOI) and 3, 5, and 7 days later] to assess pharmacokinetics (PK) and pharmacodynamics (PD) of a bolus of lispro insulin (0.15 U/kg) when delivered using an insulin pump.
 
Upon completion of the first wear period (after 7 days or sooner, in the event that infusion set change out has occurred) and a 7-21 day washout period, participants will return to the investigational clinic site and will have a second infusion set inserted by a qualified professional. Sequence of control and investigational infusion set will be randomized.
 
It is expected that infusion set change out may be required prior to the end of the 7 day wear period. If necessary, participants will follow written instructions for change out to a commercial CSII set and return to the study center for visual and photographic evaluation of the insertion site. CGM data will be available to the study site in real time (and will be reviewed at each clinic visit) by using Dexcom Clarity software to access the individual participant’s Dexcom cloud account data. Data will be downloaded from the participant’s

--	--

	blood glucose and ketone monitors at the completion of each treatment period. Participants who require change out of their infusion set during the first 7-day study period will still be eligible to participate in the second study period. End-of-study will occur at the end of the second 7-day study period (or sooner, if infusion set change out is required prior to completion of the second 7-day period).
Study Duration:	Estimated duration of the study is 6–12 months to allow for patient screening and obtaining informed consent from up to 30 potential participants, and 2 treatment periods of up to one week (7 days) each.
Participant Duration:	Patient participation is estimated at 7 weeks (± 1 week): 
 • Up to 3 weeks for screening, enrollment/randomization, and 1 week adjustment period with Dexcom G6® study CGM • 1-week Treatment Period 1; • 2-week washout/rest (± 1 week); • 1-week Treatment Period 2.
Investigator(s)/ Study Sites:	[name] President & CEO, AMCR Institute [name] [contact] E-mail: [contact]

1.2 SCHEMA

[figure not shown]

Figure 1: Schematic overview over study design.

1.3 SCHEDULE OF ACTIVITIES (SOA)

Table 2: Schedule of Activities

	Screening	Treatment Period 1				Washout Period		Treatment Period 2				
Study Visit	Visit 0	Visit 1	Visit 2	Visit 3	Visit 4	Telephone Follow-up	Washout	Visit 5	Visit 6	Visit 7	Visit 8	Telephone Follow-up
Day	-28 to -1	0A	3A	5A	7A	7±1 after Period 1	8-28	0B	3B	5B	7B	7±1 after Period 2
Time after CSII insertion [h]			72±3	120±3	168±3				72±3	120±3	168±3	
Procedures	Screening	Rand. / Insertion/ Clamp	Clamp	Clamp	Clamp	Phone call	Routine	Enrollment/ Insertion/ Clamp	Clamp	Clamp	Clamp	Phone call
Example Day of Week		Fri	Mon	Wed	Fri			Fri	Mon	Wed	Fri	
Labs/Questionnaires/Instructions												
Informed consent	X											
Demographics	X											
Medical history	X											
Urine Pregnancy test ¹	X	X						X				
Physical exam (incl. height/weight) ²	X							X				
Concomitant medication review	X	X	X	X	X	X		X	X	X	X	
CBC	X											X
HbA1c	X											
C-Peptide	X											
Basic Metabolic Panel	X											
ECG	X											
Vital signs ³	X	X	X	X	X			X	X	X	X	
Randomization		X										
Patient Instructions ⁴	X	X	X	X	X	X		X	X	X	X	
Adverse event review and evaluation ⁵	X	X	X	X	X	X		X	X	X	X	
Device Applications/Removals												
Download Pump and SMBG Data	X	X	X	X	X			X	X	X	X	
Insert CGM sensor	X	X						X				
Review CGM data	X	X	X	X	X				X	X	X	
Remove Participant's infusion set (AM of clamp procedure), insert CSII catheter (abdomen)		X						X				

Remove CSII catheter (& insert patient's routine CSII set)					X ⁶						X ⁶	
--	--	--	--	--	----------------	--	--	--	--	--	----------------	--

Clamp											
Switch pump to 0.1 U/h at when IV insulin is started (evening before clamp procedure)		X	X	X	X				X	X	X
Insert 2 IV cannulas for insulin and dextrose infusion (evening before clamp procedure)		X						X			
Prime tubing with insulin and connect to CSII infusion set and then prime cannula		X						X			
PK/PD study (run-in, bolus, clamp)		X	X	X	X			X	X	X	X
Venous sample BG/serum insulin ⁷		X	X	X	X			X	X	X	X
Patient meal (at end of clamp procedure) ⁸		X	X	X	X			X	X	X	X
Others											
Evaluate insertion site ⁹		X	X	X	X	X		X	X	X	X
Video insertion		X						X			
Record CGM and CSII performance issues		X	X	X	X			X	X	X	X

¹ Pregnancy test required for all female participants of child-bearing age without documented menopausal status or removal of key organs.

² Only the Visit 1 body weight value will be used to calculate insulin doses and infusion rates for both treatment periods

³ Vital signs include BP (seated or recumbent), pulse, respiratory rate and temperature; VS should be done every 2 hours ± 30 min during clamp procedures

⁴ Ascensia Contour Next glucose monitor and Precision Xtra blood ketone monitor with respective test strips will be provided.

⁵ 100 mm Visual Analog Scale (VAS) pain assessment to be performed at Achilles infusion set insertion, daily during home wear period, and at time of Achilles infusion set removal.

⁶ End-of-Study (EOS) and Early Termination (ET) Assessments; if participant terminates early because of cannula failure event then glucose clamp will not be done if failed cannula has been removed. Study completion time may differ per participant. Study is considered complete at the end of the second wear period as determined by: **(1) Participant has worn Achilles infusion sets for 7 days, (2) Participant experiences Achilles set failure requiring change out to commercial CSII set, (3) Participant has hyperglycemic event requiring at home change out to commercial CSII set, or (4) Resolution of device or procedure-related AEs.**

⁷ Blood for clamping decisions every 5-15 min for 300 min

⁸ Meal and individually determined bolus dose of insulin delivered via pump bolus performed in clinic; participants may be discharged home shortly after meal is completed. The same meal and insulin bolus dose (unless clinically indicated that bolus dose should be modified) to be provided for each participant after all clamp studies

⁹ Insertion Site Evaluations for each wear period: Day 0 pre-infusion set insertion and after securing post-insertion; Daily during Day 0 to +7 wear period; Day 7 (or upon infusion set failure) pre-infusion set removal, post-infusion set removal. The site personnel will perform photographic documentation of the insertion site at the time of insertion and at the time of presentation to the study site at the end of each wear period.

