6.1.1.7 HOME CSII TREATMENT PHASE

During the home CSII treatment phase participants will use the investigational/control CSII catheter in combination with the Medtronic MiniMed insulin pump for diabetes management. Participants will follow their regular lifestyle, adjusting basal infusion rate, meal bolus doses and correction doses according to their routine clinical methods. They will use their diabetes diaries to document VAS pain score, signs/symptoms of hypoglycemia, treatment of hypoglycemia, CSII catheter issues, and overall health. BG will be measured continuously by the CGM device.

Study participants will receive detailed instructions regarding diabetes care plan, including dietary guidelines, treatment of hyperglycemia, hypoglycemia, and the management of CSII catheter failure. Participants will be instructed to monitor their blood ketone levels if their CGM or SMBG values are greater than 250 mg/dL for more than 2 hours or they develop signs/symptoms of diabetic ketoacidosis.

Table 7: Participant instruction for at home use

Patient Diary (daily)	Participant records: 
 ▪ Hypo-/hyperglycemic episodes ▪ Insertion site assessments ▪ Insertion set failure ▪ Other device issues or complications ▪ VAS Pain Scale (daily insertion site comfort levels)
Insertion Site Assessment (daily)	Participant visually inspects and records insertion site findings (i.e. skin reaction or infection)
Dexcom G6® CGM	Records glucose values throughout study

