9.4.4 SAFETY ANALYSES

Tolerability of infusion sets will be assessed by comparing the mean VAS scores from day of insertion through Day 7 of use with a mixed-effects (repeated-measures) linear model with treatment, period and day as fixed effects and participant as a random effect. The mean difference between treatments will be compared with a two-sided test using significance level $\alpha=0.05$.

Adverse events (AEs) will be coded using CTCAE v4.0. Descriptive statistics (number of participants and per-participant incidence) for device-related AEs will be presented by System Organ Class, Preferred term, severity and treatment. Unanticipated and serious device-related AEs will be presented separately by treatment.

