4.3.3.2 Visual Analog Scale (VAS) for Pain Assessment

The VAS score will be normalized to 100 mm based on the reported pain score length and the total line length.

The mean VAS score of each subject is calculated as:

$$\text{Mean VAS} = \frac{\text{Sum of (all available VAS Score)}}{\text{\# of all available VAS Score}}$$

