4.4.5.6 VAS

VAS pain score will also be presented descriptively.

Population	Safety
------------	--------

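### Insertion and removal pain scores are scheduled for the Achilles set only; if sites followed that literally, the SAP's pooled VAS means for the two sets are not comparable

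*Protocol*

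**What the plan says.** **Schedule.** Footnote 5 of Table 2 (Protocol 1.3) is the only text that schedules a pain score at insertion or removal. The assessment is "to be performed at Achilles infusion set insertion, daily during home wear period, and at time of Achilles infusion set removal". The daily scores are not tied to a device. Protocol 6.1.1.7 has participants record VAS pain in their diaries during a home phase in which "participants will use the investigational/control CSII catheter", and Table 7 makes this a daily entry. Daily scores are therefore expected on both sets.

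**Endpoints.** The synopsis lists two VAS endpoints under safety: "Mean visual analog scores (VAS) scores (0-100 mm) from Day of insertion through Day 7 of use" and "Mean difference of VAS scores (0-100mm) of CSII investigational sets and CSII control sets". The second needs control data that can be set against the Achilles data.

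**Planned analysis.** Protocol 9.4.4 plans to assess tolerability as follows: "comparing the mean VAS scores from day of insertion through Day 7 of use with a mixed-effects (repeated-measures) linear model". Its fixed effects are day, period and treatment; participant is random; and the test is two-sided at 0.05.

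**SAP.** Section 4.3.3.2 introduces its formula with "The mean VAS score of each subject is calculated as"; the formula is the sum of all available scores divided by their number, with no separation of insertion, daily and removal scores. Section 4.4.2 splits descriptive summaries by treatment and period. Section 4.4.5.6 says "VAS pain score will also be presented descriptively" and plans no model. Section 2.5, which lists departures from the protocol's statistical section, covers early termination and the dropped interim analysis but not the VAS change.

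**The concern.** The endpoint is a comparison between sets, so both means should be built from the same time points. Read literally, footnote 5 gives Achilles two scores per wear period that control does not have. Those two come from moments (needle insertion, adhesive and cannula removal) when pain may differ from pain during wear. An unweighted mean of all scores turns that difference in timing into an apparent difference between devices.

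Two features of the SAP add to this. The protocol model includes day, which would take out part of a timing imbalance; a plain mean takes out none. And a summary by treatment and period specifies no within-participant difference, so the comparative endpoint has no defined estimate in the SAP.

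What is at stake is how one tolerability endpoint is read. The primary slope analysis and the sample size do not depend on VAS.

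**Working it through.** The documents state no VAS mean, SD, power or sample size, so there is no figure of the plan's to reproduce. The check is algebra on the SAP's mean, followed by a look at what the protocol model would have done.

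**Step 1: the formula.** Suppose the two sets cause identical pain. Let D be the mean daily score on either set, I and R the insertion and removal scores (recorded for Achilles only), and k the number of daily Achilles scores.

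- Achilles mean = (kD + I + R)/(k + 2)
- Control mean = D, whatever its number of daily scores
- Artefact (Achilles minus control) = (I + R − 2D)/(k + 2)

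The artefact is positive if I + R > 2D, zero if they are equal, and negative if daily pain is the higher.

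**Step 2: numbers.** All scores below are assumptions, in mm. k = 7 stands for daily scores on Days 1 to 7. k = 2 stands for a set that failed early; Protocol 9.4.1 expects 40-50% of sets to fail.

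| D | I | R | k = 7 | k = 2 |
|---|---|---|---|---|
| 5 | 5 | 5 | 0/9 = 0 | 0/4 = 0 |
| 5 | 15 | 10 | 15/9 = +1.7 | 15/4 = +3.75 |
| 5 | 20 | 10 | 20/9 = +2.2 | 20/4 = +5.0 |
| 5 | 30 | 20 | 40/9 = +4.4 | 40/4 = +10.0 |
| 10 | 5 | 5 | −10/9 = −1.1 | −10/4 = −2.5 |

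Counting a Day 0 daily score as well (k = 8) changes little: 0, +1.5, +2.0, +4.0 and −1.0.

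**Step 3: the protocol model.** The fixed effects of Protocol 9.4.4 (treatment, period, day as a factor) were fitted by least squares to noise-free data for a 24-participant crossover. Participant was entered as a block, and there was no true device difference. The treatment coefficient is then the artefact that remains.

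| D, I, R | No control score on Day 0 | Daily Day 0 score on both sets |
|---|---|---|
| 5, 5, 5 | 0 | 0 |
| 5, 15, 10 | +0.45 | +1.15 |
| 5, 20, 10 | +0.45 | +1.54 |
| 5, 30, 20 | +1.36 | +3.08 |
| 10, 5, 5 | −0.45 | −0.77 |

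In the first column the insertion score has no effect (+0.45 for both I = 15 and I = 20), because Day 0 exists for Achilles alone and the day effect absorbs it. In the second column most of the artefact stays: +3.08 against +4.0 for the SAP mean with k = 8. The model protects in part only.

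**Step 4: matched time points.** If all three kinds of score exist on both sets, or the comparison uses only those that do, the artefact is 0 mm when there is no true difference.

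**The case against.** The strongest reply is that footnote 5 is a drafting slip and that control insertion and removal scores were collected too. The text gives this real support. The footnote is attached to the adverse event review row, which is marked in both treatment periods, and by crossover every participant wears control in one of them. The endpoint window opens on the day of insertion, and the protocol model covers that window by treatment. Footnote 6 on the same table is equally loose: one of its criteria for the end of the second wear period is "Participant has worn Achilles infusion sets for 7 days", although participants who had Achilles first wear control then.

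This reply makes the literal reading uncertain but does not remove the point. No other text schedules a control insertion or removal score. Footnote 9 of the same table speaks neutrally of the infusion set in each wear period, so a site could take footnote 5 at its word. Even under the generous reading, the SAP pools unlike scores without a check that both sets contributed them.

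A second reply is that description alone is reasonable after termination at the seventh completer. That is fair for a test at 0.05. But the SAP does not give this reason for VAS, it keeps mixed models for the PK and PD parameters, and section 2.5 does not list the change.

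A third reply is that rewording the footnote cannot alter data already collected. That is correct, so the SAP change is the part that matters for this study.

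**Conclusion.** The point holds conditionally. As written, footnote 5 can give the two sets different VAS time points, and the SAP's unweighted mean would then not compare like with like. Under the assumed scores the artefact runs from about −1 to +4 mm with seven daily scores and from −2.5 to +10 mm with two.

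A reader might infer that the VAS comparison is biased against Achilles. The documents do not support that. It would require that sites skipped control insertion and removal scores, which is not established, and that I + R exceeds 2D. Protocol 2.3.1 calls slight discomfort at cannula insertion common, which makes the second condition plausible for insertion, but no VAS values are given and nothing bears on removal. A reader might also infer that restoring the protocol model would cure the problem; Step 3 shows that it would not.

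The unlisted move from a model to a descriptive summary is a separate, smaller documentation gap that stands however footnote 5 is read. The primary endpoint is unaffected.

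**What to change.** - **Protocol, footnote 5.** Replace Achilles infusion set by study infusion set (Achilles or control) for insertion and removal. This settles the intended schedule and serves any reuse of the protocol; it does not change data already collected.
- **SAP 4.3.3.2.** Derive insertion, daily and removal VAS as three separate summaries per participant and treatment. State how many of each exist for each set.
- **SAP 4.4.5.6.** Restrict the between-set comparison to time points collected on both sets, and report the within-participant difference with a 95% CI.
- **SAP 4.4.5.6 and 2.5.** Either keep the model of Protocol 9.4.4 for that comparison, or record in section 2.5 that a descriptive summary replaces it and why.

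The cost is a little more tabulation and some wording. With about seven completers the intervals will be wide and should be presented as such.
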